8.12 Biomarker Blood Sample Collection and Processing

Four 10 mL green-top heparinized tubes of blood will be collected pre-dose via venipuncture for biomarker analysis at multiple time points. These will be collected on Day 1 of Cycles 1, 2 and 4. All tubes will be sent to the Hematologic Procurement Laboratory, one tube (for flow cytometry) will be forwarded at ambient temperature to [name] in the Department of Flow and Image Cytometry at RPCI. Plasma and PBMCs will be separated within 2 hours following extraction. These samples will be stored and analyzed by [name].

The other three tubes will be processed in the Hematologic Procurement Laboratory. Plasma samples are to be processed at 4°C using a refrigerated centrifuge at approximately 3000 rpm for about 10 minutes with the plasma being aliquoted into 2 cryovials per time-point. The samples will immediately be frozen at -70°C or below until analyzed. PBMC's will then be obtained by ficoll gradient as per the lab's standard procedure. Two of the tubes will be pooled and the PBMC's will be frozen in Gibco Cell culture freezing media and will be stored in LN2 until time of analysis. The remaining tube of PBMC's will be frozen in RNA later and will be stored in -70 degrees or below until analyzed. The screw cap polypropylene cryogenic tubes will be labeled with the clinical study number, participant's MR number, participant's study number, protocol time point, protocol day, date and time of draw. Samples will be analyzed in RPCI's Department of Flow and Image Cytometry:

Roswell Park Cancer Institute
Department of Flow and Image Cytometry Cancer Cell Center, C317
Attn: [name]
Refer to Study Number– I 274515
[contact]
[contact]
[contact]
[contact]

Note: All investigator or analyzing research laboratories housing research samples need to maintain current Temperature Logs and study-specific Sample Tracking and Shipping Logs. The Principal Investigator/Laboratory Manager must ensure that the stated lab(s) have a process in place to document the receipt/processing/storage/shipping of study-related samples/specimens. This is required for both observational and interventional clinical studies collecting clinical samples.

NETWORK SITES: Four 10 mL green-top heparinized tubes of blood will be collected pre dose via venipuncture for biomarker analysis at multiple time points. These will be collected on Day 1 of Cycles 1, 2 and 4. The samples will be labeled with the Subject ID # (unique to Network patients), initials, clinical study number, protocol time point, dose, protocol day, date and time of draw. As above, the whole blood samples will be kept on ice until shipping and shipped on cold packs.

Whole blood samples will be shipped via Fed Express Overnight on cold packs with delivery on Tuesday-Friday. **NO SATURDAY DELIVERY.** Do not ship on a Friday or the day before a holiday.

Samples should be shipped to:
Roswell Park Cancer Institute
Hematologic Procurement Laboratory
Basic Science Bldg., S524
Attn: [name] / [name]
Refer to Study Number– I 274515
[name]
[name]
[contact]

Prior to shipment, please email the following individuals:

[contact],
[contact],
[contact], [contact] and
[contact].

Email should include FedEx number and inventory of what is in the shipment.

8.13 Pathology

Fresh tumor biopsies will be obtained on study, one within 30 days prior to Cycle 1 Day 1 and one within 7 days of Cycle 4 Day 1; biopsy prior to C4D1 is preferred, but may be after C4D1, if necessary. Biopsies can be obtained from any tumor site, though a metastatic site is preferred, e.g. via US guided liver biopsy. Four tumor cores, preferably 16-18 gauge and 1 cm long, will be obtained at each time point, with one core being formalin fixed and paraffin-embedded for later IHC staining, and the remainder kept fresh at 4°C for further processing in [name] laboratory.

8.13.1 Archived Formalin-Fixed Paraffin Embedded (FFPE) Biopsy Samples

Note: Participants for whom newly-obtained samples cannot be provided (e.g. inaccessible or subject safety concern) may submit an archived specimen only upon agreement from the Principal Investigator). This does not apply for the last 10 patients enrolled on the study, where a fresh biopsy will be mandatory.

The following sections of tissue from the most recent neoplastic tissue that exists in the Paraffin Archive in the Department of Pathology (or outside institution) will be collected:

1. Ten unstained sections cut at 4 microns on plus glass slides.
2. One H&E stained section

The study coordinator or designee will be responsible for entering the order into the EMR using the standard format for all clinical trial pathology requirements.

For **Network Sites**, de-identified tissue samples using study-specific subject ID number and tissue accession# (GCP requires at least 2 identifiers) are to be sent to RPCI Correlative Science Pathology Office (Attn: Protocol Lab Team). The **shipping label** should read as follows:

Roswell Park Cancer Institute
[name]
Correlative Science Pathology Office, GBSB S-636
Attn: Protocol Lab Team (I 274515 Samples)
[name]
[contact]

Please email: [contact] when samples are being shipped. Email should include FedEx number and inventory of what is in the shipment.

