Pre-clinically, the success of anti-EGFR inhibition has been additionally linked to immune mechanisms (11-13). The down-regulation of MHC Class I expression, which is associated with reduced antigen processing, is linked to poor survival and loss of inflammatory response in colorectal cancer (14). Decreased MHC Class I expression is also associated with EGFR over-expression and activation of RAS signaling; the EGFR-RAS-MAPK pathway is known to be a driving pathway in colorectal cancer pathogenesis. Research for some time has suggested a link between effective cancer control through EGFR inhibition and an intact host immune system, though clinically this has been more difficult to establish. Interestingly, in preclinical models, EGFR inhibitors upregulate MHC Class I and II gene expression (15). Further, in various pre-clinical models, EGFR inhibitors are capable of inducing a tumoral lymphocytic infiltrate. This is seen in colon cancer tumor spheroids, as well as murine models using the 7A7 murine anti-EGFR antibody. In these same situations, depletion of CD4+ and CD8+ cells abrogates the efficacy of anti-EGFR therapy (11). In recently data presented by [name] group, the hepatic resection specimen of colorectal cancer patients who were treated with anti-EGFR therapy demonstrated the most robust CD3+, CD8+ and CD45RO+ lymphocytic infiltrates (as compared to chemotherapy alone)(16). In summary, the anti-EGFR anti-tumor effect is mediated in part through immune mechanisms and is capable of increasing tumor infiltrating lymphocytes. As such, there is reason to think that an anti-EGFR targeting antibody may increase tumor infiltrating lymphocytes, which might prove synergistic when combined with additional therapies which may limit intrinsic tumor immune suppression.

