- Objective tumor response using irRECIST (**Appendix D**)
-

Exploratory Endpoints

- Tumor and immune cell biomarkers (using IHC):
 - PD-1, PD-L1
 - Tumor infiltrating and stromal lymphocytes
 - Additional biomarkers to evaluate mechanisms of EGFR and PD-1 resistance will be evaluated in exploratory analysis
- Tumor immune cell populations (via flow cytometry)
 - Regulatory T cell populations.
 - Tumor infiltrating lymphocyte, monocyte and NK cell populations.
 - Myeloid derived suppressor cell populations.
- Peripheral blood biomarkers (flow cytometry and ELISA):
 - Cytokines (including IFN γ and IL-10) and additional circulating factors (including sPD-L1)
 - Regulatory T cell populations.
 - Tumor infiltrating lymphocyte, monocyte and NK cell populations.
 - Myeloid derived suppressor cell populations.

All participants will sign an informed consent prior to study related tests. All participants will meet the inclusion and exclusion criteria summarized in **Section 5.1** and **Section 5.2**.

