5 PARTICIPANT SELECTION

5.1 Inclusion Criteria

To be included in this study, participants must meet the following criteria:

1. Have a pathologically confirmed diagnosis of colorectal cancer, which is metastatic or otherwise unresectable.
2. Have received at least 1 prior systemic therapy in the metastatic or unresectable disease setting. Patients who have recurred within six months of adjuvant chemotherapy are not required to have received an additional line of chemotherapy.

3. RAS wild-type. Both KRAS and NRAS testing are necessary. The presence of pathogenic mutations in KRAS or NRAS is exclusionary. Primary tumor or metastatic tumor may be tested.
4. Appropriate for anti-EGFR therapy: Naive to anti-EGFR therapy (cetuximab or panitumumab) or a candidate for rechallenge by virtue of the following:
 - a. the investigator deems anti-EGFR retreatment with cetuximab to be a reasonable standard of care option AND
 - b. outcome of prior anti-EGFR therapy was not rapid progression (i.e. ≤ 3 months on therapy) AND
 - c. prior anti-EGFR therapy was administered > 6 months prior to the start of protocol therapy
5. Age ≥ 18 years of age.
6. Have an ECOG Performance Status ≤ 2 . Refer to Appendix B.
7. Have measurable disease per RECIST 1.1 criteria present.
8. Be willing to provide tissue from a newly obtained core or excisional biopsy of a tumor lesion. Newly-obtained is defined as a specimen obtained up to 30 days prior to initiation of treatment on Day 1.
9. Have the following clinical laboratory values (all screening labs must be performed within 14 days of treatment initiation):
 - Hemoglobin ≥ 8 g/ dL
 - Absolute neutrophil count $\geq 1000/ \text{mm}^3$
 - Platelet count $\geq 100,000/ \text{mm}^3$
 - Serum creatinine clearance ≥ 15 mL/min (refer to Appendix C: Cockcroft-Gault Equation).
 - Serum total bilirubin ≤ 1.5 ULN or, direct bilirubin \leq ULN for participants with total bilirubin levels > 1.5 ULN.
 - AST (SGOT) and ALT (SGPT) ≤ 2.5 ULN or, ≤ 5 ULN for participants with liver metastases.
10. Female participants of childbearing potential are to have a negative serum pregnancy test.

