13 CORRELATIVE DATA ANALYSIS

Biomarker Analyses: Pre- and post-treatment levels and changes from pre- to post-treatment in biomarkers will be summarized overall and by response and 6-month PFS categories using summary statistics (e.g., mean or median, with dispersion measures, and using transformed values as appropriate). Depending on the number of responses, logistic regression models may be used to compare response rates across pre-treatment biomarker levels. Proportional hazards models may be used to examine progression-free survival and overall survival across biomarker levels.

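### Archived tissue can stand in for the fresh baseline biopsy, and Section 13 does not separate the two, so tumour IHC values that pre-date intervening therapy can be pooled as pre-treatment values

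*Combined protocol and SAP*

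**What the plan says.** Inclusion criterion 8 (Section 5.1) asks for willingness to give a fresh core or excisional biopsy: "Newly-obtained is defined as a specimen obtained up to 30 days prior to initiation of treatment on Day 1". Section 4.1.1 makes the pre-treatment biopsy mandatory. It makes the Cycle 4 biopsy optional, except for the final 10 patients.

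Section 8.13.1 then gives an exception. Participants who cannot provide a fresh sample, for example because the tumour is inaccessible or biopsy is unsafe, "may submit an archived specimen only upon agreement from the Principal Investigator". The tissue is to be taken "from the most recent neoplastic tissue that exists in the Paraffin Archive". The section sets no maximum age and does not require that the block was collected after the last therapy. It adds: "This does not apply for the last 10 patients enrolled on the study, where a fresh biopsy will be mandatory".

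Section 13 states: "Pre- and post-treatment levels and changes from pre- to post-treatment in biomarkers will be summarized overall and by response" and by 6-month PFS category. It also allows logistic models of response on pre-treatment biomarker levels, and proportional hazards models of PFS and OS across biomarker levels. It does not mention specimen source.

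**The concern.** A pre-treatment biomarker value should describe the tumour as it stood when study treatment began. A fresh biopsy within 30 days of Day 1 does that. An archived block may not, because this population is pretreated. Inclusion criterion 2 requires prior systemic therapy in the metastatic or unresectable setting, or recurrence within six months of adjuvant chemotherapy. Inclusion criterion 4 admits rechallenge patients who have already had cetuximab or panitumumab.

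The protocol itself gives reason to expect that such therapy alters the markers. Section 1.2 reports that liver resection specimens from patients given anti-EGFR therapy "demonstrated the most robust CD3+, CD8+ and CD45RO+ lymphocytic infiltrates" compared with chemotherapy alone. Tumour-infiltrating and stromal lymphocytes by IHC are a listed exploratory endpoint in Section 4.1.1. If a block pre-dates such therapy, part of an apparent pre-to-post change may belong to the earlier treatment. A baseline value related to response, PFS or OS may likewise describe a tumour state that no longer existed at enrolment.

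**Working it through.** The documents give no figure for the biomarker analysis, so there is none to reproduce. The check asks whether archived tissue can reach the analysis, which analyses it can reach, and how much it could matter.

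**1. Route into the analysis.** Section 8.13.1 offers archived tissue as the substitute when a newly obtained sample is unavailable, and the documents state no other use for it. In Table 4, footnote 16 on the baseline tumour biopsy cell refers to Sections 8.12.1 and 8.12.2. No such sections exist, and the reference appears to mean 8.13.1 (archived) and 8.13.2 (fresh). Section 13 neither includes nor excludes archived specimens.

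**2. Which analyses are exposed.**
- Tumour IHC (PD-1, PD-L1, lymphocytes): exposed, because archived slides can be stained.
- Tumour flow cytometry: not exposed. Section 8.13.2 uses fresh cores, so an archived baseline leaves this value missing rather than biased.
- Blood markers: not exposed. Section 8.12 draws the baseline sample before dosing on Cycle 1 Day 1.
- Primary response and 6-month PFS tests: not exposed, because no tissue marker enters them.

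**3. Ceiling on archived baselines.** Total patients minus the last 10:
- at the target of 42: 42 − 10 = 32, and 32/42 = 76%;
- at the minimum of 38: 38 − 10 = 28, and 28/38 = 74%.

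The actual share is not given.

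**4. Bias in a mean.** Let f be the share of analysed baselines that are archived, and A the mean shift in the marker between the archive date and enrolment, in standard deviations. An archived value lies A below the Day 1 value on average, so the mean baseline is off by −f × A and the mean pre-to-post change by +f × A. Neither f nor A is in the documents; the values below are assumptions.

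| f | A = 0.25 SD | A = 0.5 SD | A = 1.0 SD |
|---|---|---|---|
| 10% | 0.025 | 0.05 | 0.10 |
| 25% | 0.0625 | 0.125 | 0.25 |
| 50% | 0.125 | 0.25 | 0.50 |
| 76% (ceiling) | 0.19 | 0.38 | 0.76 |

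The assumed range therefore runs from about 0.03 to 0.76 SD. Among the last 10 patients f = 0, and this bias is zero.

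**5. Change versus level.** A change score also needs the Cycle 4 biopsy, which is optional before the final 10 patients and less likely where tumour could not be reached or safely sampled at baseline. For change scores, f is therefore probably near the bottom of the table. Baseline summaries and the models on pre-treatment levels need no second biopsy, so every archived baseline could enter them.

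**The case against.** The strongest reply is that nothing in the documents says archived tissue is analysed as the pre-treatment level. A reader might infer this from the silence of Section 13 and from footnote 16. The footnote cites sections that do not exist, however, and the heading of 8.13.2 reserves the words pre- and on-treatment biopsies for the protocol cores. This stands: what the documents show is that such pooling is permitted, not that it is planned.

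A reader might also take 76% as the likely share of archived baselines. The documents do not support that. The pre-treatment biopsy is mandatory by default, willingness to provide fresh tissue is an inclusion criterion, and the exception needs both an inability to provide a sample and the Principal Investigator's agreement.

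Nor can a percentage of contaminated pairs be derived from the 4-month median PFS in Section 1.2. The documents give neither a count of archived baselines nor an uptake rate for the optional biopsy. Being progression-free at week 9 is also not the same as being available for biopsy: Section 8.13 prefers the biopsy before Cycle 4 Day 1, and Section 6.5 allows treatment past first progression.

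Three further limits stand. The most recent block may post-date the relevant therapy, so an archived value is not necessarily wrong. Fresh biopsies may also come from any tumour site (Section 8.13), so restricting to fresh pairs does not remove differences due to site. And nothing in the documents shows that archive use differs between response groups.

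The reply does not remove the gap. Section 13 as written allows both kinds of specimen into the same summaries and models, and for baseline-level analyses the optional second biopsy gives no protection.

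**Conclusion.** The point holds in a limited form. Archived tissue with no age limit may replace the fresh baseline for all but the last 10 patients, and Section 13 pools baseline values without regard to source. Tumour IHC values that pre-date intervening systemic or anti-EGFR therapy can therefore be counted as pre-treatment values. The number affected is unknown, with a ceiling of 32 of 42. The bias is f × A, and its size rests wholly on assumed values of f and A. The main exposure is in the baseline IHC summaries and the models of response, PFS and OS; change scores are probably little affected. All of this is exploratory, and the models are optional. No primary test, sample size or safety rule changes. The correction should be made because it is cheap and, with few patients, a handful of non-contemporaneous baselines could alter a descriptive result.

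**What to change.** In Section 13:
- restrict tumour IHC pre-to-post change to pairs in which both samples are fresh protocol biopsies;
- summarise archived baselines separately;
- run the IHC baseline-level models on fresh baselines as the main analysis, with archived values added as a sensitivity analysis.

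On the specimen form, record specimen type, collection date and site, and therapy received since collection. For archived samples sent by network sites, Section 8.13.1 specifies only the subject ID and tissue accession number as identifiers. Prior therapy is already taken in the medical history (Section 8.2), so therapy since collection can be derived once the collection date is known. Report biopsy site for fresh samples too. Correct the section numbers in footnote 16 of Table 4.

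The cost is a few sentences, a few form fields and slightly fewer values in an exploratory analysis. No patient has an extra procedure.

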8.13.2 Pre-and On-Treatment Biopsies

Formalin-Fixed Paraffin-Embedded (FFPE) Biopsy Samples

Immediately fix one core in 10% neutral buffered formalin then paraffin-embed as per institutional standard. If the entire FFPE core biopsy block cannot be submitted, then submit a minimum of eight unstained sections cut at 4 microns on plus glass slides plus one H&E stained section.

Label the block or slides with the study-specific subject ID number and a second identifier, such as the tissue accession number.

The FFPE specimen should be sent to RPCI Correlative Science Pathology Office (Attn: Protocol Lab Team), where the specimens will be batched until later analysis in RPCI's Core Pathology Laboratory. For **Network Sites**, ship block or slides to:

Roswell Park Cancer Institute
Correlative Science Pathology Office, GBSB S-636
Attn: Protocol Lab Team (I 274515 Samples)
[name]
[name]
[contact]

Please email: [contact] when samples are being shipped. Email should include FedEx number and inventory of what is in the shipment.

Viable Fresh Biopsy Samples

The **additional core biopsy samples** will be placed in 10-mL cold sterile RPMI 1640 supplemented with 10% human serum and with final concentrations of penicillin G (100 units/mL) and streptomycin (100 µg/mL) and kept at 4°C. Label the samples with study-specific subject ID number, clinical study number, protocol time point and, protocol day. Samples will be analyzed by [name], CCC 317, in the Department of Flow and Image Cytometry.

Network Sites should ship the cold samples overnight with an ice pack to:

Roswell Park Cancer Institute
Department of Flow and Image Cytometry
Cancer Cell Center, C317
Attn: [name]
Refer to Study Number– I 274515
[name]
[name]
[contact]

Please email: [contact], [contact] and [contact] when samples are being shipped

Email should include FedEx number and inventory of what is in the shipment.

Note: All investigator or analyzing research laboratories housing research samples need to maintain current **Temperature Logs** and study-specific **Sample Tracking and Shipping Logs**. The Principal Investigator/Laboratory Manager **must** ensure that the stated lab(s) have a process in place to document the receipt/processing/storage/shipping of study-related samples/specimens. This is required for both observational and interventional clinical studies collecting clinical samples (ship Monday to Thursday only).

9 EFFICACY EVALUATIONS

9.1 Objective Tumor Response

All protocol-defined imaging studies must be performed at the investigative site or sponsor-approved facility using protocol-defined parameters. The same method of assessment and the same technique should be used to characterize each identified and reported lesion at baseline and during follow-up. Primary objective tumor response will be assessed according to irRECIST (Appendix D).

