Objectives	
Primary:
 
 To estimate the objective response rate of patients with metastatic colorectal cancer treated with pembrolizumab and cetuximab. To estimate the 6-month progression-free survival (PFS) rate of patients with metastatic colorectal cancer treated with pembrolizumab and cetuximab. To examine the adverse event profile of combining pembrolizumab and cetuximab. 
Secondary:
 
 To examine the PFS of patients with metastatic colorectal cancer treated with pembrolizumab and cetuximab. To determine the objective response rate by immune-related response criteria (irRECIST) of patients with metastatic colorectal cancer treated with pembrolizumab and cetuximab To examine the overall survival of patients with metastatic colorectal cancer treated with pembrolizumab and cetuximab. 
Exploratory:
 
 To identify tumor and peripheral blood biomarkers of response and/or resistance to the study treatment.
Study Design	Phase Ib/II study, single arm, multi-institutional study.
Target Accrual and Study Duration	We will target 42 eligible and treated patients, but will require at least 38 eligible and treated patients. An initial 9 patient phase Ib study is planned to ensure safety of the combination. This will be followed by further enrollment of 33 patients on the phase II study. It is expected that this study will enroll 1-2 patients per month. With this accrual rate, this study is anticipated to finish accrual in 4 years. Assuming a minimum of 6 months of follow-up in all patients, the study will take 4 years to complete in total.
Study Procedures	
Disease Evaluation: CT chest/abd/pelvis (or acceptable alternative) every 9 weeks (+/- 7 days)
 
Physical Examination (including vital signs, and body weight): Baseline, Day 1 of all Cycles, End of Treatment, Safety Follow-Up

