3.2 Secondary/ Exploratory Objectives

- To examine the PFS of patients with metastatic colorectal cancer treated with pembrolizumab and cetuximab.
- To determine the objective response rate by immune-related response criteria (irRECIST) of patients with metastatic colorectal cancer.
- To examine the overall survival of patients with metastatic colorectal cancer treated with pembrolizumab and cetuximab.

[figure not shown]

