4.1.1 Phase Ib\II

There will be an initial phase Ib cohort to examine the safety and tolerability of the combination. Study progress will be monitored regularly by the RPCI Phase I Committee. After up to 9 patients are enrolled, and a minimum of 6 have completed at least two cycles of chemotherapy, the study will be suspended, and the safety/tolerability of the combination will be examined. At that time, the study team will decide what action to take, e.g., continue the study as is, make changes to the study with regard to treatment or dose modifications, or discontinue the study. Once analysis is complete and a safe treatment plan has been established, the phase II study will commence.

The Phase II study will enroll patients with metastatic colorectal cancer who are eligible for anti-EGFR therapy (i.e. RAS wt, no known expanded KRAS or NRAS mutations, anti-EGFR therapy naïve or appropriate for anti-EGFR rechallenge). For the purposes of the study, a cycle will be defined as three weeks. Patients will be treated with cetuximab, administered weekly and pembrolizumab, administered every 3 weeks as described in **Section 6**. A regimen of pre-emptive skin care is recommended, as described in **Section 6.4**. Disease assessments will occur every 9 weeks to assess response, using RECIST v 1.1. As described in **Section 6.1**, after initial progressive disease, if fulfilling certain criteria, patients may continue on therapy with further response assessments in line with irRECIST criteria (**Appendix D**). Per local policy, a consent addendum should be obtained to continue on treatment past progression. Progression free survival and objective response rate will be observed. Additional blood based biomarker tests will be performed prior to treatment, at 4 weeks (cycle 2, day 1) and 10 weeks (cycle 4, day 1). A mandatory biopsy will be performed prior to treatment; a secondary biopsy at approximately 10 weeks (cycle 4, day 1) will be optional, but strongly encouraged. However, in order to obtain sufficient samples for informative analysis, for the final 10 patients of the study, both biopsies will be mandatory.

Primary Endpoints

- Six-month progression free survival and objective tumor response rate will be evaluated according to RECIST 1.1 guidelines after every 3 cycles (9 weeks) of treatment.

- Adverse events will be categorized and graded according to NCI CTCAE v4.0.

Secondary Endpoints

- Progression-free survival
- Overall survival

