12 STATISTICAL METHODOLOGY

This is a single-arm phase Ib\II study of pembrolizumab and cetuximab in patients with metastatic colorectal cancer.

The primary objectives of this study are:

- To estimate the objective response rate of patients with metastatic colorectal cancer treated with pembrolizumab and cetuximab
- To estimate the 6-month progression-free survival (PFS) rate of patients with metastatic colorectal cancer treated with pembrolizumab and cetuximab
- To examine the adverse event profile of combining pembrolizumab and cetuximab

The secondary (exploratory) objectives of this study are:

- To examine the PFS of patients with metastatic colorectal cancer treated with pembrolizumab and cetuximab
- To examine the overall survival of patients with metastatic colorectal cancer treated with pembrolizumab and cetuximab
- To determine estimate the objective response rate by immune-related response criteria (irRECIST) of patients with metastatic colorectal
- To explore peripheral blood and tumor biomarkers of response and/or resistance to the study treatment

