12.1 Sample Size Determination

We utilize two primary efficacy endpoints for this study: the proportion of patients achieving complete or partial RECIST objective response rate and the proportion surviving progression-free for at least six months. While the addition of pembrolizumab to cetuximab may have cytotoxic effect, it may act primarily in a cytostatic fashion; therefore, it is important to consider both endpoints, and thus declare the agent worthy of further investigation if it shows activity on either endpoint. We utilize a single-stage version of the bivariate design of Sill, et al (24) (2012). Based on historical data, the response rate for cetuximab alone in this patient population is approximately 20%, and the proportion of patients surviving progression-free for at least six months is approximately 30% (5). We set the following null and alternative hypotheses indicating inactivity or activity for the two endpoints.

Endpoint	H₀ (regimen inactive)	H₁ (regimen active)
Objective tumor response	20%	40%
6-Month PFS	30%	50%

We will target 42 eligible and treated patients, but will require at least 38 eligible and treated patients in order to have $\geq 80\%$ power to detect activity based on response alone, $\geq 80\%$ power to detect activity based on 6-month PFS alone, and $\geq 97\%$ power if the regimen is active on both endpoints. This assumes independence of the two endpoints; slight losses of power occur for moderate dependence between the two endpoints. Type I error is controlled at < 0.10 . An exact binomial test will be used to compare the observed response and 6-month PFS percentages versus the null values in the table above. Only patients who are not treated with study therapy will be replaced.

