12.3 Efficacy Analysis

Objective tumor response and six-month PFS will be tabulated and will be compared to the null values using exact tests. All treated patients with study therapy will be considered evaluable for response and 6-month PFS. Patients who receive at least one full dose of both drugs and come off study therapy prior to 6 months and receive off-protocol therapy will be considered treatment failures with regard to the 6-month PFS endpoint. Patients who have infusions reactions to cetuximab, such that continuation of treatment is not deemed feasible, will be replaced.

All patients treated with study therapy will be considered evaluable for response and 6-month PFS. Patients who come off study therapy prior to 6 months and receive off-protocol therapy will be considered treatment failures with regard to the 6-month PFS endpoint. Objective tumor response will not be considered after patient receives off-study therapy.

Objective tumor response using immune-related RECIST (irRECIST) will be tabulated.

Analysis of secondary endpoints will be hypothesis generating and descriptive in nature. Distributions of PFS and OS will be estimated using the Kaplan-Meier method.

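### Section 9.1 assigns irRECIST to the primary objective response, while the primary endpoint list names RECIST 1.1 and five other places keep irRECIST response out of the primary test

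*Combined protocol and SAP*

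**What the plan says.** Section 9.1, which opens the efficacy evaluation chapter, states: "Primary objective tumor response will be assessed according to irRECIST (Appendix D".

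Section 4.1.1 says otherwise under its Primary Endpoints heading: "Six-month progression free survival and objective tumor response rate will be evaluated according to RECIST 1.1 guidelines". Section 12.1 and the statistical paragraph of the synopsis define the tested endpoint as "the proportion of patients achieving complete or partial RECIST objective response rate", with no version of RECIST.

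Five places put irRECIST response outside the primary endpoint:

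- Synopsis, secondary objectives: "To determine the objective response rate by immune-related response criteria (irRECIST) of patients with metastatic colorectal cancer treated with pembrolizumab and cetuximab".
- Section 3.2, which repeats that objective under its secondary/exploratory heading.
- Section 4.1.1, secondary endpoints: "Objective tumor response using irRECIST".
- Section 12, which lists it among the secondary (exploratory) objectives.
- Section 12.3: "Objective tumor response using immune-related RECIST (irRECIST) will be tabulated". This comes after the exact test of response, for which that section names no criterion.

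**The concern.** Two criteria are assigned to one primary endpoint. Read literally, Section 9.1 makes the primary response endpoint the same as the secondary irRECIST endpoint. It also sends an assessor to Appendix D, although Sections 9.2 to 9.5, which follow directly, give RECIST-type rules.

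Under Section 12.1 the regimen is declared worth further study if it shows activity on either response or 6-month PFS, so a few patients classified differently could decide the trial. It is an open-label, single-arm study. With the conflict unresolved, the criterion could be settled after the responses are known.

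**Working it through.** **1. Do the two rule sets differ, on the documents' own text?**

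| Feature | Sections 9.2 to 9.5 | Appendix D (irRECIST) |
|---|---|---|
| New lesion | Progression | New measurable lesions are added to total measured tumor burden and are not progression in themselves |
| Non-target progression | Unequivocal progression | Higher bar: the worsening must also be massive |
| Confirmation of CR | Required, at least 6 weeks later | Not mandatory for irCR |
| Confirmation of PR | Required, at least 6 weeks later | Silent for irPR, so Section 9.5 may still apply |
| End of the best-response window | Disease progression or recurrence, or study discontinuation (Section 9.4) | Unclear under Section 9.1 whether progression means RECIST 1.1 PD or irPD |

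A patient can therefore fall on both sides. Suppose a new measurable lesion gives RECIST 1.1 PD, and the patient is clinically stable and stays on treatment under Section 6.5. Total burden, including the new lesion, later falls at least 30% below baseline. Non-target disease has not progressed, and no new non-measurable lesion has unequivocally progressed. Under Section 9.1 read literally this is a responder. Under RECIST 1.1 it is not.

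**2. Reproducing the stated design**

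Inputs from Section 12.1: response 20% versus 40%; 6-month PFS 30% versus 50%; target n = 42, minimum n = 38; independent endpoints; success on either; type I error below 0.10; power at least 80% (response alone), 80% (PFS alone) and 97% (both). No cut-offs are stated, and I took the test as one-sided.

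For cut-offs r (responses) and s (progression-free at 6 months):

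- αR = P(X ≥ r | n, 0.20) and αP = P(X ≥ s | n, 0.30)
- Type I error = 1 − (1 − αR)(1 − αP)
- Power, response alone = 1 − (1 − P(X ≥ r | n, 0.40))(1 − αP), and likewise for PFS alone and for both

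A search over cut-offs leaves exactly one pair that meets every target at each n:

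| n | r / s | αR | αP | Type I error | Power: response / PFS / both |
|---|---|---|---|---|---|
| 42 | 14 / 18 | 0.0298 | 0.0526 | 0.0808 | 0.859 / 0.864 / 0.979 |
| 38 | 12 / 17 | 0.0623 | 0.0388 | 0.0986 | 0.895 / 0.804 / 0.977 |

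For n = 42: 1 − (0.9702)(0.9474) = 0.0808. The stated design is reproduced.

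**3. Illustration: what a looser criterion could do**

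Assumption, with no source in the documents: irRECIST raises an inactive regimen's response rate from 20% to 22% or 25%, and the PFS endpoint is unaffected.

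| n | Inactive response rate | αR | Type I error, either endpoint |
|---|---|---|---|
| 42 | 22% | 0.0610 | 0.110 |
| 42 | 25% | 0.1430 | 0.188 |
| 38 | 22% | 0.1120 | 0.146 |
| 38 | 25% | 0.2228 | 0.253 |

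For n = 42 at 22%: 1 − (0.9390)(0.9474) = 0.110. The 0.10 limit is reached at an inactive rate of 21.4% for n = 42 and 20.1% for n = 38.

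With no assumed rise, one reclassified patient at my n = 42 cut-off still turns the response decision: P(X ≥ 13) = 0.062 and P(X ≥ 14) = 0.030 under 20%.

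**The case against.** The strongest reply is that the intent can be recovered. Section 4.1.1 names RECIST 1.1 twice, once for the 9-weekly assessments and once for the primary endpoints. Sections 4.1.1 and 6.5 both bring in irRECIST only after first progression. Sections 9.2 to 9.5 are RECIST-type, and a separate irRECIST table in Section 12.3 would be redundant if irRECIST were primary. On this view Section 9.1 is a drafting slip, and a statistician working from Sections 4 and 12 would use RECIST 1.1.

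As a reading of intent I accept this, and it supports the fix. It does not remove the conflict. Section 9.1 speaks of the primary response, not of management after progression, and no text overrides it. A primary endpoint should not be settled by counting which statement appears more often.

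The objections to the arithmetic also stand in part. The 22-25% range has no source. The documents do not say which criterion lies behind the 20% null, so no direction of bias is shown. The 20.1% threshold at n = 38 mainly reflects a type I error that already starts at 0.0986. One patient at the boundary matters under any binary rule. How often patients would be classified differently cannot be known from the documents.

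**Conclusion.** The concern holds and must be fixed before analysis. Section 9.1 gives a criterion for a decision-driving primary endpoint that contradicts the protocol's own primary endpoint list and five other places, and the two criteria can classify the same patient differently.

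The severity rests on that contradiction. It does not rest on proven inflation of false positives. The type I error figures are illustrations that depend on my cut-offs, a one-sided test, independent endpoints and an assumed rise in the inactive response rate.

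**What to change.** Replace the sentence in Section 9.1 with text to this effect:

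> The primary response endpoint is determined by RECIST 1.1, with confirmation as in Sections 9.2 to 9.5. irRECIST (Appendix D) applies to the secondary response endpoint and to assessments after RECIST 1.1 PD (Section 6.5). For the primary endpoint, the best-response window in Section 9.4 closes at RECIST 1.1 PD, and responses first met after that date do not count.

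A response met before RECIST 1.1 PD but not confirmed by then should be covered in the same place. Section 9.2 already lists unconfirmed responses as stable disease, so a cross-reference is enough.

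In Section 12.1 and the synopsis, write RECIST 1.1 in place of RECIST. Section 12.3 then takes its criterion from Sections 9.1 and 12.1, and naming it there too would remove any doubt.

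The cost is a few sentences. Section 6.5 already has sites identify progression by RECIST 1.1 first, so no scan, patient, sample size, error rate or treatment rule changes.
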